### **8.5.2 Secondary Efficacy Analyses**

Descriptive statistics and 90% confidence intervals will be reported for the SALT score (observed values, relative change, and absolute change) at each time point for each dosing regimen and by subtype. By-patient data listing will also be presented for patient SALT scores. The mean of observed value, absolute change, and relative change SALT scores along with 90% confidence intervals for each dosing regimen will be presented using line graphs.

Responders at 90%, 75%, and 50% by visit will be summarized with proportions and 90% confidence intervals (using the binomial approximation with a Wald continuity correction). Responders are defined as patients with at least 90%, 75%, or 50% reduction in SALT score by visit. Percent reduction is calculated as the baseline SALT score minus the current value, divided by the baseline value, multiplied by 100. Responders will be presented graphically by dosing regimen as a bar graph at 24 Weeks and as a line graph across time.

Responses to the patient satisfaction question will be summarized with proportions and 90% confidence intervals (using the binomial approximation with a Wald continuity correction). Responses will be also categorized as “Satisfied” (including responses of “Very satisfied,” “Mostly satisfied,” and “Somewhat satisfied”) and “Dissatisfied” (including responses of “Very dissatisfied” and “Dissatisfied”) and presented as a 2 x 2 shift table from baseline to Week 24. Response will also be listed in the by-patient data listings.

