For the 4 mg cohort, 21% of patients achieved a $\geq 50\%$ reduction in their overall SALT score from baseline, however these differences were not significantly different from placebo. In the primary analysis, the response observed in the 8 mg twice-daily dose was significantly different than the 4 mg twice daily dose ($p < 0.05$) (Figure 3). The average baseline SALT score across all patients enrolled in the trial was approximately 88.

Figure 3: Primary Analysis: Responders by Visit

CTP-543 was generally well tolerated and there have been no serious adverse events reported. The most common adverse events reported across treatment groups (4 mg, 8 mg, and placebo)

were headache, upper respiratory tract infection, cough, acne and nausea. For the upper respiratory tract infections, there was a higher incidence in the placebo group. In terms of hematologic changes, there were only 3 incidents of Grade 3 or 4 changes and these 3 cases were distributed equally across the dose groups including placebo.

The 12 mg dosing cohort is currently ongoing.

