11.4.2. Efficacy

For the primary efficacy endpoint and other continuous measures, a 90% confidence interval for the dosing regimen difference at Week 24 will be calculated using the t-distribution. For categorical measures (e.g. proportion of responders), a 90% confidence interval for the dosing regimen difference at Week 24 will be calculated based on normal approximation for the binomial distribution, using the Wald continuity correction $[(1/n_1 + 1/n_2)/2]$.

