### **3. GENERAL ANALYSIS AND REPORTING CONVENTIONS**

The following is a list of general analysis and reporting conventions to be applied to this study, unless otherwise specified.

All data displays (tables, listings, and figures) will have a header showing the sponsor company name, protocol number, page number, and display status (i.e. “DRAFT” or “FINAL”), as well as a footer indicating file name and run date/time. Summary tables and data listings will be summarized by dosing regimen and overall, as appropriate. All data collected per-protocol and all derived variables will be listed.

Categorical variables will be summarized using counts (n) and percentages (%) and will be presented in the form “n (xx.x).” If a count is 0, 0% will be shown for the percentage. If a percentage is 100%, 100% will be shown with no decimal place. To ensure completeness, summaries for categorical variables will include all categories, even if no patients had a response in a particular category. Unless otherwise specified, the denominator for each percentage will be based on the number of patients in the population being summarized (header n). If missing values are present, counts will be shown but will not be included in percentage calculations.

Continuous variables will be summarized using mean, standard deviation (SD), minimum, maximum, median, and number of patients. The mean and median will be reported to an additional level of precision than the original observations, and the SD will be reported to two additional levels of precision than the original observations. The minimum and maximum will be the same precision as the original data. In general, any calculated values, such as those due to unit conversion, will be rounded to the same number of decimal places as the original data.

Confidence intervals will be 90%. No formal hypothesis tests will be performed. Testing will be performed only for the Treatment Period. Estimates and confidence intervals may be reported to 1 more decimal than the original data.

Summary tables and data listings:

- No preliminary rounding will be performed; rounding will only occur after analysis.
- Data from patients excluded from an analysis population will be presented in the data listings but will not be included in the calculation of summary statistics, where applicable.

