## **8.4 Overview of Efficacy Analysis Issues**

### **8.4.1 Handling of Dropouts or Missing Data**

The Last Observation Carried Forward (LOCF) approach will be implemented for missing SALT score data, e.g., if the SALT score in the Week 16 visit window is missing, the next and closest available on-treatment SALT score measurement before the Week 16 visit window will be used for all remaining SALT assessments: Week 16, Week 20 and Week 24. Missing baseline values will not be carried forward. If a SALT assessment is missing between two non-missing SALT

assessments visits, the SALT score at that visit will be interpolated using the mean of the closest pre- and post-assessments.

If the number of discontinuations due to adverse events is substantial, other methods will be explored.

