**Table 8-1 Efficacy Variables and Analysis Methods**

Efficacy Variables	Collection Times	Method
Primary		
SALT (relative change)	Baseline, Week 24	Mean and 90% confidence interval (t-distribution)
Secondary		
Responder Analysis	Baseline, Week 4, 8,	Proportion and 90%
SALT (90%, 75%, 50% relative reduction)	12, 16, 20, 24	confidence interval (binomial approximation)
SALT (absolute change)	Baseline, Week 4, 8, 12, 16, 20, 24	Mean and 90% confidence interval (t-distribution)
SALT (relative change)	Baseline, Week 4, 8, 12, 16, 20, 24	Mean and 90% confidence interval (t-distribution)
Satisfaction of hair coverage	Baseline, Week 24	Proportion and 90% confidence interval (binomial approximation); Shift table
Exploratory		
VAS for Eyebrows (percent change)	Baseline, Week 24	Mean and 90% confidence interval (t-distribution)
Satisfaction of hair coverage quality	Baseline, Week 24	Proportion and 90% confidence interval (binomial approximation); Shift table
SALT ( $\leq 10$ , $\leq 20$ , $\leq 25$ absolute score)	Baseline, Week 4, 8, 12, 16, 20, 24	Proportion and 90% confidence interval (binomial approximation)

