### **8.5.3 Exploratory Efficacy Analyses**

VAS for Eyebrows scores will be summarized using percent change from baseline at Week 24. Descriptive statistics will be presented with 90% confidence intervals around the mean (t-distribution). Results will also be listed in the by-patient data listings.

The satisfaction of hair quality questions will be summarized with descriptive statistics at baseline and Week 24, and will be listed in the by-patient data listings. Responses to the patient satisfaction question will be summarized as proportions with 90% confidence intervals. Responses will be also categorized as “Satisfied” (including responses of “Very satisfied,” “Mostly satisfied,” and “Somewhat satisfied”) and “Dissatisfied” (including responses of “Very dissatisfied” and “Dissatisfied”) and presented as a 2 x 2 shift table from baseline to Week 24.

Additional analyses by dosing regimens will be performed at Weeks 4, 8, 12, 16, 20, and 24 for patients who achieve an absolute SALT score of  $\leq 10$ ,  $\leq 20$ , or  $\leq 25$ . Responders by visit will be summarized with proportions and 90% confidence intervals (using the binomial approximation with a Wald continuity correction).

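### Read per regimen, the planned 90% Wald interval collapses to ±1/(2n) when nobody responds, and the supplied plan has no rule for that case (minor)

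*SAP*

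**What the plan says.** SAP 8.5.2 summarises patients with at least 90%, 75% or 50% SALT reduction, visit by visit, with "proportions and 90% confidence intervals (using the binomial approximation with a Wald continuity correction"). It uses the same method for the hair-coverage question. SAP 8.5.3 repeats it for SALT scores of at most 10, 20 and 25 at Weeks 4 to 24: "Responders by visit will be summarized with proportions and 90% confidence intervals (using the binomial approximation with a Wald continuity correction"). For the hair-quality questions, 8.5.3 says only "Responses to the patient satisfaction question will be summarized as proportions with 90% confidence intervals", and Table 8-1 gives the label "confidence interval (binomial approximation").

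SAP Section 3 adds that "summaries for categorical variables will include all categories, even if no patients had a response in a particular category". Its only rule for a zero count is to print 0% as the percentage; it says nothing about the interval.

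The correction is written out in one place. For categorical measures, Protocol 11.4.2 plans a 90% interval for the Week 24 regimen difference, "calculated based on normal approximation for the binomial distribution, using the Wald continuity correction", with the term (1/n1 + 1/n2)/2. The SAP gives no one-sample form and does not say outright that its intervals are per regimen.

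**The concern.** A Wald interval takes its width from the observed proportion. When nobody responds, the estimated variance is zero and the printed limits come from the continuity correction alone. The same happens in mirror image when everyone responds.

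Empty cells are plausible here. The plan reports six SALT thresholds at six visits in arms of about 30, starting at Week 4, and also the separate levels of five-level satisfaction items. Entry requires SALT of at least 50, and Protocol 4.4.1 gives a mean baseline of about 88 in the earlier trial. From 88, a 90% reduction means a score of 8.8 or lower.

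What is at stake is how such a cell reads. A table showing 0% with an upper limit under 2% tells the reader that higher rates are excluded, which 30 patients cannot show.

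**Working it through.** The documents state no numerical limit for any proportion, so there is no figure of the plan's own to reproduce first.

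**Inputs**
- Level: 90% two-sided (SAP Section 3), so z = 1.645 and z² = 2.706.
- n = 30: planned patients per regimen (SAP 2.2). This is the main case for SALT, because "The Last Observation Carried Forward (LOCF) approach will be implemented for missing SALT score data" (SAP 8.4.1).
- n = 25: completers per group (SAP 2.6).
- One-sample correction: 1/(2n). This is the standard form and the counterpart of the protocol's two-sample term. It is an assumption, because the SAP does not write it out.

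**Step 1. Limits at zero responders, per regimen**
- Plan: p ± [z√(p(1−p)/n) + 1/(2n)]. At p = 0 this is ±1/(2n): 1/60 = 1.67% at n=30, and 1/50 = 2.0% at n=25.
- Wilson upper limit: z²/(n+z²). This is 2.706/32.706 = 8.3% at n=30, and 2.706/27.706 = 9.8% at n=25.
- Clopper-Pearson upper limit: 1 − 0.05^(1/n). This is 9.5% at n=30 and 11.3% at n=25.
- Ratio to the planned limit: 5.0 (n=30) and 4.9 (n=25) against Wilson; 5.7 at both sizes against Clopper-Pearson. Against a Jeffreys interval it is 3.7.

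**Step 2. How fast the problem fades (upper limits, n=30)**

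| Responders | Plan | Wilson | Clopper-Pearson |
|---|---|---|---|
| 0 | 1.7% | 8.3% | 9.5% |
| 1 | 10.4% | 13.6% | 14.9% |
| 2 | 15.8% | 18.3% | 19.5% |
| 3 | 20.7% | 22.6% | 23.9% |

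From one responder upwards the planned limit is only 1.1 to 1.4 times too low.

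**Step 3. If the interval is for the regimen difference instead**

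With both arms empty, the protocol's term gives ±(1/n + 1/n)/2 = ±1/n: 3.3 points at n=30 and 4.0 at n=25. Newcombe's interval at 0 against 0 is plus or minus the Wilson upper limit: 8.3 and 9.8 points. The planned interval is then about 2.5 times too narrow (8.3/3.3).

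**Step 4. Chance of an empty cell**

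The documents give no early-visit rates, so these rates are assumptions. The probability is (1−p)^30: 74% at a true rate of 1%, 55% at 2% and 21% at 5%.

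**Step 5. Coverage of the planned interval (exact binomial enumeration)**
- n=30, assumed rates: 100% at 1%, 45% at 2%, 60% at 3%, 78% at 5%, 84% at 6%, 91% at 8%. The 2% figure is essentially 1 − 0.98^30, because every empty cell misses the true rate.
- Coverage at n=30 is below 85% for rates of about 1.7–6.3%, where a count of zero misses. It is below 85% again at about 10.4–11.2%, where counts of zero and one both miss (the upper limit at 1/30 is 10.4%).
- At reported rates: Protocol 4.4.1 states "For the 4 mg cohort, 21% of patients achieved a" reduction of at least 50% in SALT, and gives 47% for 8 mg BID. Coverage there is 88.8% and 90.2% at n=30, and 89.6% and 92.9% at n=25. Wilson at n=30 gives 88.6% and 90.2%.

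**The case against.** **The reading is not fixed.** The correction is spelled out only for the regimen difference, and SAP Section 12 lists no departure from that. This stands as a condition on the size: ±1/(2n) and the factors of 5 and 5.7 hold only per regimen. That reading is still the better fit, since 8.5.2, 8.5.3 and Table 8-1 speak of a proportion with its interval. The collapse occurs under either reading.

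**The hair-quality questions.** A reader might infer that, with no correction named, their interval has zero width at a zero count. The documents do not support this. Table 8-1 uses the same label for SALT responders and the hair-coverage question, both of which carry the correction in 8.5.2, and Protocol 11.4.2 applies it to categorical measures in general. An omitted parenthesis is the likelier explanation. What remains is that the method should be stated.

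**A rule may exist elsewhere.** Table specifications sit in a separate attachment that was not available, and SAP Section 3 does not itself say that an interval is printed for an empty category. This limits the claim to the supplied text.

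**The consequence is small.** No test or decision depends on these intervals, and the count is printed beside them. A reader might infer that the responder intervals are unsound in general. Steps 2 and 5 do not support that: the distortion is modest from one responder upwards, and coverage is adequate at the reported rates.

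**Wilson is not better everywhere.** That is correct. At n=25 and a 10% rate it covers 83%, against 92% under the plan. This argues for allowing a rule limited to extreme cells.

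**Conclusion.** The point holds, at minor severity. Read per regimen, a zero-count cell would carry an upper limit of 1.7% at n=30 (2.0% at n=25), where standard methods give 8.3–9.5% (9.8–11.3%). If the interval is for the difference, two empty arms give one about 2.5 times too narrow. This rests on the usual 1/(2n) correction and on there being no overriding rule in the table shells. How often it would happen is unknown, because the empty-cell probabilities use assumed rates. Only descriptive secondary and exploratory intervals are affected; the primary analysis uses a t-interval.

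There is a separate consistency point, which adds no weight to this one. On the per-regimen reading, the SAP describes no interval for the Week 24 responder difference that Protocol 11.4.2 specifies. SAP Section 1 says that changes from protocol-specified analyses will be documented, but Section 12 lists only the added SALT thresholds.

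**What to change.** In SAP 8.5.2, 8.5.3 and Table 8-1:
- Specify 90% Wilson limits for single proportions, or Clopper-Pearson if guaranteed coverage is preferred. At a minimum, do so for cells with 0 or n responders.
- Apply one stated method to SALT responders, the hair-coverage question and the hair-quality questions.
- State that these intervals are per regimen.
- Record the change in SAP Section 12.

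Separately, restore the Protocol 11.4.2 interval for the Week 24 responder difference in SAP 8.5.2, or list its omission in Section 12. A Newcombe or Miettinen-Nurminen form is optional.

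The cost is SAP wording and a standard software option, with no new data. There is a statistical price. Wilson coverage can dip to about 81% at n=30: its lower limit at 1/30 is 0.75%, so a true rate of 0.7% is covered only when nobody responds, and 0.993^30 = 81%. Clopper-Pearson is conservative, with 93–99% coverage at the rates checked.

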16.2. Patient Satisfaction Questions

16.2.1. Satisfaction of Hair Coverage Question

How satisfied are you with the hair coverage on your scalp today?

- 0 Very dissatisfied
- 1 Dissatisfied
- 2 Somewhat satisfied
- 3 Mostly satisfied
- 4 Very satisfied

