### **8.2 Secondary Efficacy Endpoints**

Secondary efficacy endpoints include:

- Proportion of patients achieving at least a 90%, 75%, and 50% relative reduction in SALT score from baseline at Weeks 4, 8, 12, 16, 20, and 24;
- Absolute change in SALT scores from baseline at Weeks 4, 8, 12, 16, 20, and 24 in the Treatment Period;
- Relative change in SALT scores from baseline at Weeks 4, 8, 12, 16, 20, and 24 in the Treatment Period;
- Change in satisfaction of hair coverage as reported by patient

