#### **8.2.1 Satisfaction of Hair Coverage**

Results of the patient satisfaction questions will be collected on Day 1 and at Week 24. Patients will answer the question “How satisfied are you with the hair coverage on your scalp today?”.

Responses range from 1-5 as follows: 1 (very dissatisfied), 2 (dissatisfied), 3 (somewhat satisfied), 4 (mostly satisfied), 5 (very satisfied).

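### Change in satisfaction with hair coverage is analysed within patients only by a 2 x 2 shift table, which hides 4 of 10 possible improvements and the size of the others

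*SAP*

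**What the plan says.** SAP 8.2 lists the endpoint as "Change in satisfaction of hair coverage as reported by patient". The question, in Protocol Appendix 16.2.1, is "How satisfied are you with the hair coverage on your scalp today". SAP 8.2.1 gives the scale: "Responses range from 1-5 as follows: 1 (very dissatisfied), 2 (dissatisfied), 3 (somewhat satisfied), 4 (mostly satisfied), 5 (very satisfied". It also gives the timing: "Results of the patient satisfaction questions will be collected on Day 1 and at Week 24". Each patient therefore contributes at most one change.

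SAP 8.5.2 plans three displays for this question:

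- response proportions with 90% confidence intervals;
- a further two-category grouping, with Satisfied ("including responses of “Very satisfied,” “Mostly satisfied,” and “Somewhat satisfied") and Dissatisfied ("including responses of “Very dissatisfied” and “Dissatisfied"), "presented as a 2 x 2 shift table from baseline to Week 24";
- a by-patient listing.

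In Table 8-1 the row "Satisfaction of hair coverage" names a proportion with interval and a shift table, and nothing else. The list of planned tables has one summary (14.2.2.3) and one shift table (14.2.2.4) for the question. Protocol 11.4.4 leaves the method for the patient-reported outcomes to the SAP.

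**The concern.** An endpoint defined as change should have an analysis that measures change. Proportions at Day 1 and at Week 24 are two margins: they do not say which patients moved, in which direction or how far. That leaves the 2 x 2 shift table as the only planned analysis of the endpoint as named, and it reduces five ordered levels to two.

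This is the only patient-reported endpoint at the secondary level. The trial compares two active regimens with the same daily total, so a difference in patient benefit may be one of degree. A table that records only whether a patient crossed from dissatisfied to satisfied cannot report degree of change. A patient who starts at somewhat satisfied or higher cannot register an improvement in it at all.

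**Working it through.** The documents give no figure for this endpoint, so there is none to reproduce. The check is a direct count.

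**Inputs.** Five ordered levels, coded 1 to 5 (SAP 8.2.1). Cut: levels 1–2 Dissatisfied, levels 3–5 Satisfied (SAP 8.5.2). One baseline and one Week 24 response per patient.

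**All 25 baseline/Week 24 pairs.** *Same* is no change on the five levels. *Shown* is a change that crosses the cut. *Hidden* is a change that the 2 x 2 table reads as none.

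| Baseline \ Week 24 | 1 | 2 | 3 | 4 | 5 |
|---|---|---|---|---|---|
| 1 | same | hidden | shown | shown | shown |
| 2 | hidden | same | shown | shown | shown |
| 3 | shown | shown | same | hidden | hidden |
| 4 | shown | shown | hidden | same | hidden |
| 5 | shown | shown | hidden | hidden | same |

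**Improvements.** Possible: 5 × 4 / 2 = 10. Crossing the cut: 2 × 3 = 6. Hidden: 10 − 6 = 4, namely 1→2, 3→4, 3→5 and 4→5.

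**Worsenings.** By symmetry, 10 possible and 4 hidden: 2→1, 4→3, 5→3 and 5→4.

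**Overall.** Pairs on the diagonal of the 2 x 2: 2 × 2 + 3 × 3 = 13 of 25. Pairs with truly no change: 5. The excess is 13 − 5 = 8 = 4 + 4.

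**Size of gain.** The six improvements that register are 1→3, 1→4, 1→5, 2→3, 2→4 and 2→5. They span one level (2→3) to four levels (1→5), and all fall in one cell.

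**Patients who start in the bottom two levels.** Open to them are 4 improvements from level 1 and 3 from level 2, so 7. One is hidden (1→2). The other three hidden improvements all start at level 3 or above. Entry requires SALT ≥ 50, so a low starting level is plausible, but the documents give no baseline distribution for this question.

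**Coding.** Protocol Appendix 16.2.1 codes the same five answers 0 to 4. The cut falls between the same answers, so the counts do not change.

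**After the change.** A 5 x 5 shift, or an improved/unchanged/worsened classification on five levels, hides 0 of 10 in each direction.

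**The case against.** The strongest reply is that the plan already shows degree. SAP 8.5.2 summarises the responses as proportions first and only then adds the two-category grouping. SAP section 3 requires categorical summaries to show every category and calls for display by regimen. Table 14.2.2.3 is separate from the shift table. The natural reading is five-level proportions by regimen.

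This stands, and it rules out two stronger readings that a reader might infer:

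- *That two regimens could appear the same although one has mostly very satisfied and the other mostly somewhat satisfied patients.* The Week 24 proportions would show that contrast.
- *That the cut costs the regimen comparison information or effective sample size.* The shift table has no stated interval and the SAP plans no formal tests, so the dichotomy is not the regimen comparison. Any such figure would also need assumed Week 24 distributions, and it would concern the margins, not within-patient change.

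It may also be said that 4 of 10 overstates the loss, because it counts transitions. That is fair, and the 1 of 7 figure belongs beside it. The cut follows the answer labels and is prespecified, and the listings would allow a finer table later. Both are true, but a listing is not an analysis, and a table chosen after the data are seen is weaker than one named now. The table shells (Attachment A) are not among the documents and could hold finer output; nothing in the SAP text or table list points to it.

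What remains is that margins, however finely divided, do not report patient-level change.

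**Conclusion.** The point holds as a mismatch between a change endpoint and its one coarse change analysis. The 2 x 2 table hides 4 of 10 possible improvements and 4 of 10 possible worsenings, and it does not separate a one-level gain across the cut from a four-level gain. If most patients start in the bottom two levels (an assumption), the hidden share is 1 of 7 and the main loss is the size of the gain.

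The conclusion rests on the SAP text, Table 8-1 and the list of tables, and on reading the proportions as five-level. The primary analysis is not affected. The change is worth making because it is cheap and lets the trial report the endpoint that it named.

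One further inference should be resisted: that Protocol 11.4.2 already provides a t-interval for mean change in category. It gives that interval for continuous measures, and the SAP treats this question as categorical. A mean would also assume equal spacing on a scale with two dissatisfied levels, three satisfied levels and no neutral one.

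**What to change.** In SAP 8.5.2, Table 8-1 and Table 14.2.2.4:

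1. Present the full 5 x 5 shift from Day 1 to Week 24 by regimen.
2. Add the number and proportion of patients improved, unchanged and worsened in category, by regimen. State the denominator (for example, Efficacy Population patients with both responses).
3. Give a 90% interval for the regimen difference in proportion improved, by the method that Protocol 11.4.2 already sets for categorical measures: normal approximation with continuity correction (1/n₁ + 1/n₂)/2.
4. Keep the 2 x 2 table as a supplementary display; it can be read off the 5 x 5.

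Reconcile the 0–4 coding in Protocol Appendix 16.2.1 with the 1–5 coding in SAP 8.2.1 in the same edit.

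The cost is SAP and shell wording; no new data are needed. The downside is sparse cells: about 30 patients per arm over 25 cells averages 30/25 = 1.2 per cell. The improved/unchanged/worsened counts are therefore the summary to read, with the 5 x 5 as supporting detail.
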